10.5.6 Other Safety Measurements

10.5.6.1 Autoimmunization

Blood samples will be taken from patients randomized to Intuvax at Vacc1 (prior to vaccination) and Sun-Start Visits to evaluate potential autoimmune events by screening of autoantibodies against clinically relevant autoantigens:

- Anti-nuclear antibodies (IF-ANA) and kidney parenchyma-associated autoantigens (liver-kidney microsomal antigens and mitochondrial antigens).

The analyses will be performed by [REDACTED]. The blood samples collected should be labelled with the patient’s unique screening number at both study visits. The study specific Laboratory Manual, which will be provided to all sites participating in this study, will include full details on blood sample collection, processing, storage, and shipping requirements. All samples will be destroyed after analyses have been performed.

The IF-ANA results will be recorded and assessed as “Negative” or “Positive”. Additional assessment of “Weak” or “Strong” will be done for positive results on Homogenous, Speckled, Nucleolar, and Centromere patterns.

10.5.6.2 Alloimmunization

Blood samples will be taken from patients randomized to Intuvax at Vacc1 (prior to vaccination) and Sun-Start Visits to evaluate potential vaccine-induced alloimmunization at the humoral level by screening of alloantibodies against HLA-A, B, C (HLA class I) and HLA-DR, DQ, DP (HLA class II) antigens.

The analyses will be performed by [REDACTED]. The blood samples collected should be labelled with the patient’s unique screening number at both study visits. The study specific Laboratory Manual, which will be provided to all sites participating in this study, will include full details on blood sample collection, processing, storage, and shipping requirements. All samples will be destroyed after analyses have been performed.

The results will be recorded and assessed as “Present” or “Not present”.

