This is the third Intuvax-study in man and the second study in mRCC patients. A phase I/II study in hepatocellular carcinoma patients is ongoing. Twelve (12) patients were included during 2012-2013 at one (1) study site in Sweden in the first phase I study in patients with mRCC referred for nephrectomy. The diagnosis was based on radiological presentation. No pretreatment biopsies from the kidney(s) were collected. Patients with prior autoimmune disease, with ongoing immunosuppressive therapy, or any other active cancer were

excluded. The patients' metastatic load varied. Five (5) patients were in the high-risk group and seven (7) in the intermediate group, according to the Heng prognostic model [4]. The Intuvax injections were performed with the patient hospitalized three (3) days to ensure safe care, collection of vital signs and blood samples. The vaccinations were performed twice, 14 days apart, in all patients. Nephrectomy was performed two (2) weeks after the second vaccination. Three (3) different dose levels of DCs; 5×10^6 , 10×10^6 , and 20×10^6 , were administered.

No serious adverse events (SAEs) related to the vaccination were noted. Transient fever reactions with duration less than one (1) day and rash was noted in 5 out of 12 patients. All patients survived the postoperative three (3) month follow-up visit. No significant deviations in blood chemistry attributable to the vaccination procedure were noted. Accidental bile duct injury was inflicted in one (1) patient resulting in transient hepatic failure. The renal function was decreased after nephrectomy in all patients as expected but no further decrease was observed except for one (1) patient who developed progressive renal function deterioration due to a previously undetected plasma cell disorder/myeloma. There were no signs of any autoimmune reactions as measured by standard tests while a humoral donor-specific alloimmunization was seen in three (3) patients.

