AEs	X	X ^c	X ^c	X	X	X	X	X ^k	X ^v	X
Diagnosis Confirmation ^f				X						

a Assessment to be completed before nephrectomy and may be done the day before nephrectomy for logistical reasons

Locally analyzed Creatinine for patients included in the study before 28 August 2017 (if performed as part of clinical routine) to be recorded in eCRF

b Height only at Screening. Weight at all visits except for Vacc1 and Vacc2 Visits.

c See specific flow chart, *Table 3*, for detailed instructions on pre- and post-vaccination assessments.

d Physical examination, ECOG performance, and samples for safety lab and urinalyses may be taken the day before vaccination for logistical reasons

Locally analyzed results for Hb, WBC, platelets, PT-INR, and APTT need to be available before vaccination

Locally analyzed results for Hb, WBC, and clinical chemistry might need to be available prior to nephrectomy

- Analysis of coagulation status at Nephrectomy is not necessary provided the patient is not on anticoagulant treatment. For patients on anticoagulants local sampling practice applies.
- e Pregnancy test in blood at Screening, and in either blood or urine at Vacc1 and Vacc2 Visits. The pregnancy test result is needed prior to each vaccination.
 - f Samples for auto- and alloimmunization analyses will be collected prior to vaccination at Vacc1 Visit. Sampling at Sun-Start Visit only applicable for patients randomized to Intuvax.
 - g To be done when the results from all assessments made are available. Telephone contact with patient to inform about treatment and timing of next study visit.
 - h The prescribed dose to be in accordance with the SmPC/USPI including any dose adjustments.
 - i Return of sunitinib not applicable at Sun-Start Visit and Distribution not applicable at End-of-Study Visit. Standard of Care applies after End-of-Study.
 - j Start of sunitinib administration will be dependent on wound healing. The time window for initiation is five (5) to eight (8) weeks after Nephrectomy.
 - k Post-study collection of survival data.
 - l If CT cannot be used for some reason, MRI is acceptable. The same modality has to be used at all visits.

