In connection with the surgery various concomitant medications such as anesthesia, fluid substitution/blood substitution are part of clinical routine and these concomitant medications should not be recorded in the eCRF. Only concomitant medications not normally used in connection with the post-operative course after nephrectomy should be recorded in the eCRF.

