13.2 Patient Records and Source Data

The origin of source data in the study will be further specified for each study site in a separate document ("Origin of Source Data").

It is the responsibility of the Investigator to record essential information in the medical records in accordance with national regulations and requirements. The following information should be included as a minimum:

- A statement that the patient is in a clinical study
- The identity of the study e.g. Study code
- Patient unique screening number and/or patient number
- That informed consent was obtained and the date
- Diagnose and date of diagnosis
- Dates of all visits during the study period
- Any information relating to AEs
- All treatments and medications prescribed/administered (including dosage)
- Date of study termination
- Patient health service identification number

The Investigator is responsible for ensuring the accuracy, completeness, legibility and timeliness of the data recorded in the eCRFs. Data reported in the eCRF that are derived from source documents should be consistent with the source documents or the discrepancies should be explained. eCRFs will be monitored on a regular basis.

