As the technology used by [REDACTED] eliminates much more the subjective measurement of CD8+ infiltration and has been technically validated, the [REDACTED] approach is widely regarded as the more accepted one in contrast to the [REDACTED] approach. Additionally, issues in the quality of the execution had been identified in the beginning of the

[REDACTED]

[REDACTED]

[REDACTED]

Evaluation of auto- and allo-immunization parameters

Auto- and alloimmunization parameters will be assessed prior to vaccination at Vacc1 Visit and at Sun-Start Visit for patients randomized to Intuvax.

Autoimmunization parameters, anti-nuclear antibodies (IF-ANA), anti-mitochondrial and anti-liver-kidney icrosomal antigens will be assessed as “Negative” or “Positive” and additional assessment of “Weak” or “Strong” will be done for positive results on Homogenous, Speckled, Nucleolar, and Centromere patterns.

Alloimmunization at the humoral level by screening of alloantibodies against HLA-A, B, C (HLA class I) and HLADR, DQ, DP (HLA class II) antigens will be assessed as “Present” or “Not Present”.

The results of auto- and allo-immunization parameters will be tabulated using general summary statistics for categorical data. In addition shift tables will be presented to summarise the changes from the assessment prior to vaccination 1, to the Sun-start visit.

TTF defined as progressing during or after treatment with Intuvax+sunitinib or sunitinib followed by the start of subsequent second line systemic therapy

TTF is defined as progressing during or after treatment with Sunitinib or Intuvax + Sunitinib followed by the start of subsequent second line systemic therapy including immune checkpoint inhibition or tyrosine kinase inhibition, and will be derived as the date of screening until start date of second line treatment following progression. Similar censoring rules as applied for PFS will be used. Patients with PD without any second line treatment will be censored at withdrawal. Similar survival statistics as applied for analysis of PFS will be conducted.

Association between Sunitinib dose density and primary and secondary endpoints

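### Alloimmunization is read from an Intuvax-only before-and-after table that spans nephrectomy, and perioperative blood products stay out of the eCRF, so antibodies from transfusion cannot be separated from vaccine-induced ones in the planned data

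*Protocol*

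**What the plan says.** **Who is sampled and when.** Protocol section 10.5.6.2: "Blood samples will be taken from patients randomized to Intuvax at Vacc1 (prior to vaccination) and Sun-Start Visits". Its purpose is "to evaluate potential vaccine-induced alloimmunization at the humoral level by screening of alloantibodies". The footnote to the flow chart in section 7.2.2 confirms that controls give no second sample: "Sampling at Sun-Start Visit only applicable for patients randomized to Intuvax".

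**What lies in between.** Section 7.2.1.4 puts nephrectomy at least 3 days after the second vaccination and within 63 days of Screening. Section 7.2.1.5 puts Sun-Start 5 to 8 weeks after nephrectomy. No alloantibody sample is scheduled between the second vaccination and surgery.

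**What is recorded.** Section 10.5.6.2 uses a two-level result, present or not present, and states no field for donor specificity. On surgery, section 9.6 says: "fluid substitution/blood substitution are part of clinical routine and these concomitant medications should not be recorded in the eCRF". It adds that only drugs outside the normal post-operative course are to be entered. The same section also has a general rule that all medication goes into the eCRF. Section 13.2 asks that the medical records contain the following: "All treatments and medications prescribed/administered (including dosage".

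**What is analysed.** Auto- and alloimmunization is a safety endpoint in SAP section 3.4. The SAP paragraph on evaluating these parameters plans categorical summaries and then: "In addition shift tables will be presented to summarise the changes from the assessment prior to vaccination 1, to the Sun-start visit". The outputs are tables 14.2.27 and 14.2.28 and listing 16.2.12.1. The visible text has no control comparison, no split by transfusion and no rule on donor specificity.

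**Prior data.** Protocol section 5.1 reports for the 12-patient phase I study that "a humoral donor-specific alloimmunization was seen in three (3) patients".

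**The concern.** A shift from not present to present between the two visits follows two vaccinations, a nephrectomy and any blood products given around it. The baseline sample removes antibodies that were there before vaccination. It does not remove those arising from surgery and transfusion afterwards. The randomized control arm, which has the same operation, could have measured that background but is not sampled. The instruction in section 9.6 then removes the one covariate that would let an analyst separate the causes within the Intuvax arm.

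The table is the trial's only planned evidence on this safety endpoint. The risk–benefit text in protocol section 5.3 speaks of HLA antibodies arising from earlier Intuvax treatment and of what they mean for later platelet transfusion. That statement depends on attribution, and the planned data do not support attribution.

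**Working it through.** The documents state no rate, precision or sample size for this endpoint, so there is no figure to reproduce. The check has two parts.

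**1. Does nephrectomy always separate the samples?**
- Shortest interval: 11 days between vaccinations (14 − 3), plus 3 days to nephrectomy, plus 35 days to Sun-Start = 49 days.
- Longest interval: first vaccination on day 2, nephrectomy on day 63, then 56 days = 61 + 56 = 117 days.
- In both cases 35 to 56 of those days follow surgery. So under the current schedule every operated Intuvax patient with both samples has surgery in the window. Intermediate-risk patients enrolled before protocol version 4.0 followed a different visit pattern (SAP section 4.1), and the timing of their second sample may differ.

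**2. How large could the transfusion share be?**

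Inputs from the documents: about 90 patients randomized 2:1, so 90 × 2/3 = 60 on Intuvax; phase I conversion 3/12 = 25% (exact 95% CI 5.5% to 57.2%).

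Assumed inputs, with no source in the documents: fraction transfused *t* = 10% to 30%; fraction of transfused patients forming HLA antibodies *s* = 5% to 30%; vaccine and transfusion acting independently; vaccine rate *v* = 25%.

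Formulas:
- background rate *q* = *t* × *s*
- converted by transfusion alone = 60 × (1 − *v*) × *q*
- all conversions = 60 × [1 − (1 − *v*)(1 − *q*)]

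| | Low end | High end |
|---|---|---|
| *q* | 0.10 × 0.05 = 0.005 | 0.30 × 0.30 = 0.09 |
| Transfusion alone | 60 × 0.75 × 0.005 = 0.225 | 60 × 0.75 × 0.09 = 4.05 |
| All conversions | 60 × (1 − 0.75 × 0.995) = 15.225 | 60 × (1 − 0.75 × 0.91) = 19.05 |
| Share of shifts | 0.225/15.225 = 1.5% | 4.05/19.05 = 21% |

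A second pair of assumed ranges, *t* = 5% to 40% and *s* = 2% to 20%, gives *q* = 0.1% to 8% and a share of 0.3% to 19%, so the ceiling is similar.

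The share depends strongly on *v*. At *q* = 0.09:
- with *v* at its lower phase I limit of 5.5%, the share is 60 × 0.945 × 0.09 = 5.10 out of 60 × (1 − 0.945 × 0.91) = 8.40, or 61%;
- with *v* at its upper limit of 57.2%, it is 60 × 0.428 × 0.09 = 2.31 out of 60 × (1 − 0.428 × 0.91) = 36.63, or 6%.

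The phase I figure is also not like for like: it counts donor-specific antibodies, whereas this trial's stated result is presence of any screened antibody. These numbers are illustrations. The structural point needs none of them: with neither *t* nor a control rate in the data set, the share cannot be estimated.

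**The case against.** **No rule labels new antibodies vaccine-induced.** A reader might infer that transfusion antibodies will be counted as vaccine-induced. The documents do not say so. The protocol speaks of potential induction, and the SAP only summarises change between visits. What stands is that the two causes are inseparable in the table.

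**The recording exclusion is limited.** A reader might infer that recording transfusions is forbidden altogether. The exclusion covers only the eCRF and only items connected with the surgery. Medical records should hold the rest, so the data are retrievable. Retrieval is not planned, however, and the general rule in section 9.6 pulls against its own surgical exception.

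**The mechanism is not established in the documents.** Section 5.3 says that red cells lack HLA expression, and the risk table there is redacted, so what the sponsor considered cannot be fully judged. This is fair, and it is why the rates above are labelled as assumptions. But that sentence concerns harm to later red-cell transfusion, not the origin of new antibodies. The same section provides for HLA-matched platelet donors, and the term blood substitution in section 9.6 is not confined to red cells.

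**The size is easily inflated.** Dividing 60 × 0.09 = 5.4 by the expected 60 × 0.25 = 15 suggests about a third. That ignores patients who would have converted on the vaccine anyway. Allowing for overlap gives 21% at the same extremes.

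**Specificity may not be lost.** The laboratory report is not visible and may name the antibody. The documents show only that the recorded result has two levels.

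**The consequence is modest.** The error overstates the vaccine's risk, which is the cautious direction for safety. The handling described in section 5.3 does not turn on the cause of the antibody. The trial is exploratory, and no test or stopping rule uses this table. All of this stands and limits the weight of the point. It does not make the table interpretable as a vaccine effect.

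**Conclusion.** The point holds as a limit on interpretation that the plan itself creates. Alloimmunization is assessed within one arm, over an interval that contains nephrectomy, with perioperative blood products kept out of the analysis data. Table 14.2.28 therefore estimates conversion after vaccination plus surgery, and the part due to transfusion cannot be separated.

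Under the assumed rates and a 25% vaccine effect, transfusion alone would account for about 0.2 to 4 of 60 patients, or about 1.5% to 21% of shifts. It may be trivial or material, and the planned data cannot show which. The conclusion rests on one premise from outside the documents, that perioperative transfusion occurs in some patients and can induce HLA antibodies. It has no bearing on the primary endpoints. It merits correction because the endpoint is a listed safety endpoint and the correction is cheap.

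**What to change.** 1. **Record the confounder.** In protocol section 9.6, exempt blood and platelet products from the items not to be recorded. Add one eCRF item: any transfusion between Vacc1 and Sun-Start (yes/no, product, date). Back-fill it from the medical records described in section 13.2, before database lock.
2. **Split the table.** Show the alloimmunization part of table 14.2.28 overall and by transfused or not transfused, as a descriptive sensitivity display. Describe the overall figure as conversion after vaccination plus surgery. Report the non-transfused result as less confounded but still uncontrolled: it selects patients on an event after vaccination and has no comparison group.
3. **Use specificity where it exists.** Where existing laboratory reports name the antibody, flag new antibodies as donor-specific or not for HLA-A, -B and -DRB1, the loci compared between donor and patient in table 14.2.26. State that antibodies to C, DQ and DP cannot be classified this way. Existing reports must be used because section 10.5.6.2 has samples destroyed after analysis.

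Sampling the control arm would have been the direct answer. With last visits planned for Q3 2019 and a 78-week study period, the last Screening falls around Q1 2018. Sun-Start follows at most 63 + 56 = 119 days (17 weeks) later. Both sampling points had therefore passed on the planned timeline when protocol version 9.0 was issued in February 2019.

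Cost: a little data entry and small table cells. No new visit, sample or assay is needed.

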10.6 Appropriateness of Measurements

Standardized methods for measurements of efficacy and safety variables will be used.

11 ADVERSE EVENTS

11.1 Definitions

11.1.1 Adverse Event

Any untoward medical occurrence in a patient or clinical trial patient administered a medicinal product and which does not necessarily have a causal relationship with this treatment.

Comment: An AE can therefore be any unfavourable and unintended sign (including an abnormal laboratory finding), symptom, or disease temporally associated with the use of an IMP, whether or not considered related to the IMP.

11.1.2 Adverse Reaction

All untoward and unintended responses to an IMP related to any dose administered.

Comment: All AEs judged by either the reporting Investigator or the Sponsor as having a reasonable causal relationship to a medicinal product qualify as adverse reactions. The expression reasonable causal relationship means to convey in general that there is evidence or argument to suggest a causal relationship.

11.1.3 Unexpected Adverse Reaction

An adverse reaction, the nature or severity of which is not consistent with the applicable product information (e.g. Investigator's Brochure for an unauthorized IMP or SmPC/USPI for an authorized product).

Comment: When the outcome of the adverse reaction is not consistent with the applicable product information this adverse reaction should be considered as unexpected.

11.1.4 Serious Adverse Event

Any untoward medicinal occurrence or effect that at any dose:

- Results in death
- Is life-threatening
- Requires hospitalization or prolongation of existing hospitalization
- Results in persistent or significant disability or incapacity
- Is a congenital anomaly or birth defect

Comments: Life-threatening in the definition of a serious adverse event (SAE) or serious adverse reaction refers to an event in which the patient was at risk of death at the time of event; it does not refer to an event which hypothetically might have caused death if it was more severe.

Medical judgment should be exercised in deciding whether an AE/reaction is serious in other situations. Important AEs/reactions that are not immediately life-threatening or do not result in death or hospitalization but may jeopardize the patient or may require intervention to prevent one of the other outcomes listed in the definition above, should also be considered serious.

11.2 Reporting of Adverse Events

Adverse event reporting and data management will be performed according to the following relevant guidelines:

- Directive 2001/20/EC (European Clinical Trial Directive),
- CPMP/ICH/E2A/377/95 (Clinical Safety Data Management: Definition and Standards for Expedited Reporting),
- CPMP/ICH/135/95 (GCP),
- 21 CFR 312.32 (FDA).

All study patients will be carefully monitored for the occurrence of AEs during the study period from Screening Visit to the completion of the End-of-Study Visit. SAEs will be collected until completion of the End-of-Study Visit or up to 30 days after last dose of IMP administered in the study, whichever occurs later.

All patients who received IMP who withdraw less than 1 month after IMP administration must have safety evaluations, defined as recording and reporting of any SAE, for 30 days after the last dose of Intuvax or Sunitinib. The Investigator will collect AEs with a non-leading question such as “have you experienced any new health problems or worsening of existing conditions” as well as reporting events directly observed or spontaneously volunteered by patients.

Clearly related signs, symptoms and abnormal diagnostic procedure results should be grouped together and reported as a single diagnosis or syndrome whenever possible.

All AEs including but not limited to events reported by the patient, or reported in answer to an open question by the Investigator or member of this team, which fall into any of the above definitions must be recorded as an AE in the eCRF and should include the following information:

- Brief description of the event (diagnosis)
- Start date (and time, if relevant)
- Stop date (and time, if relevant) (or resolution)
- Severity
- Action taken regarding IMP
- Opinion on causality
- Seriousness
- Outcome

The general term “Progressive Disease” (PD) should not be used when reporting an AE. Instead, all symptoms, laboratory findings etc. including those that could be a reflection of PD should always be reported.

Severity describes the intensity of an event, and will be assessed using the NCI CTCAE version 4.0 [2]. The CTCAE displays Grades 1 through 5 with unique clinical descriptions of severity for each AE based on this general guideline. The term Grade refers to the severity of the AE. The following grades are used:

Grade 1 (Mild)

Asymptomatic or mild symptoms OR clinical or diagnostic observations only OR intervention not indicated.

Grade 2 (Moderate)

Minimal, local or noninvasive intervention indicated OR limiting age-appropriate instrumental Activities of Daily Living (ADL). (Instrumental ADL refer to preparing meals, shopping for groceries or clothes, using the telephone, managing money, etc.)

Grade 3 (Severe or medically significant but not immediately life-threatening)

Hospitalization or prolongation of hospitalization indicated OR disabling OR limiting self-care ADL. (Self-care ADL refer to bathing, dressing and undressing, feeding self, using the toilet, taking medications, and not bedridden.)

Grade 4 (Life-threatening consequences)

Urgent intervention indicated.

Grade 5 (Death related to AE)

If an AE changes in severity, the worst severity should be reported.

Causality

Causality will be assessed as:

Probable

A clinical event, including laboratory test abnormality, with a reasonable time sequence to administration of the IMP, unlikely to be attributed to concurrent disease or other drugs or chemicals, and which follows a clinically reasonable response on withdrawal (dechallenge). Rechallenge information is not required to fulfil this definition.

Possible

A clinical event, including laboratory test abnormality, with a reasonable time sequence to administration of the IMP, but which could also be explained by concurrent disease or other drugs or chemicals. Information on IMP withdrawal may be lacking or unclear.

Unlikely

A clinical event, including laboratory test abnormality, with a temporal relationship to IMP administration which makes a causal relationship improbable, and in which other drugs, chemicals or underlying disease provide plausible explanations.

Follow-up of Patients after Adverse Events

Any AE that is ongoing when the patient is withdrawn from the study should be followed up until the AE is resolved or the Investigator decides that the AE is stable and needs no further follow-up.

Abnormal Laboratory Values/Vital Signs

The reporting of abnormalities as both laboratory/vital signs findings and AEs should be avoided.

An asymptomatic abnormal laboratory/vital sign finding should only be reported as an AE if it is clinically significant, if it fulfils the criteria for an SAE or if it causes the patient to discontinue the study.

If an abnormal laboratory/vital sign value is associated with clinical signs and symptoms, the sign/symptom should be reported as an AE and the associated laboratory/vital sign result should be considered additional information.

Safety Evaluation 30 Days after Last Dose of Investigational Medicinal Product

All patients who have received IMP will have a safety evaluation, i.e., recording of SAEs for 30 days after last dose of IMP. The safety evaluation will be performed either as (i) a visit to

the clinic by the patient, (ii) a phone call to the patient by site personnel, or, if contact with the patient is not possible for any reason, (iii) as a review of the patient's medical records. All SAEs detected during the safety evaluation will be recorded in the eCRF and reported to [REDACTED] Drug Safety in accordance with the procedure presented in *Section 11.3*.

